## **6.0 Risks**

There are no immediate or direct benefits to those participating in this study. Clinical symptoms may be reduced through MBCT or MBSR. It is felt that the benefit of the knowledge to be gained outweighs the potential minimal risks noted below.

More specifically, we anticipate that this work will enhance our understanding of the mechanisms by which MBCT and MBSR function to reduce symptoms in a subset of depressed and anxious patients. This study will also contribute important information concerning optimization strategies for individualized treatment of depression and anxiety. Physical risk to participants is minimal. With plans to restrict access to the data as described above, other risks appear small (although impossible to quantify accurately), and potential societal benefits (in increased medical knowledge) large, including new diagnostic strategies, avenues of treatment, and perhaps prevention. The risk-benefit ratio is thus quite favorable.

**Activity:** Researchers will draw a total of 20 mL of blood per participant through venipuncture over the course of this study.

**Risk(s):** Minor pain, redness, soreness, bruising, or infection at the needle stick site; rarely, some people faint

**Risk Minimization:** Prior to drawing blood, participants will be screened in accordance with best practices set forth by the American Red Cross (as noted previously in the Specimen Collection subsection). Participants will also be encouraged to drink at least two glasses of water and consume a snack prior to each draw.

**Activity:** Participants will be asked to provide IIHI.

**Risk(s):** Breach of confidentiality

**Risk Minimization:** All IIHI and self-report data will be securely stored in REDCap. Only the PI and study coordinator will have/authorize access to IIHI and unique identifiers (e.g., subject ID numbers) linking participants to de-identified data. Behavioral data, fMRI scans, and blood samples will be identified by subject ID numbers only and will be stored separately from IIHI. Published data will in no way identify individual participants or disclose their identities.

**Activity:** Answering questions (via self-report) regarding personal history or current health status, especially with regard to psychobehavioral functioning.

**Risk(s):** Possible invasion of privacy or probing of information which might be considered sensitive

**Risk Minimization:** All members of the research team will be sensitive to the needs of participants by reminding them that they do not need to answer any questions that they would prefer not to answer, complete any tasks that they would prefer not to complete, or follow through with any procedure that they would rather decline. Study staff will use their clinical judgment to discontinue assessment if a participant appears upset.

Notably, suicidal ideation is probed in the BDI-II (item 9). Endorsement of any response other than a 0 (indicative of no suicidal ideation) will automatically prompt an email alert to the PI, the study coordinator, [name], JD, MSN, PMHNP-BC (psychiatric nurse practitioner who has 12+ years of experience diagnosing and treating people with a wide range of psychiatric disorders, including depression), and [name]., clinical psychologist at the Osher Center. Follow-up to assess risk and clarify an action plan for protecting the participant will occur within 24 hours and is detailed in the attached suicide safety plan.

**Activity:** Completion of an eight-week psychobehavioral intervention.

**Risk(s):** Risks associated with psychotherapy are minimal. Participants may experience discomfort while talking about their symptoms, emotions, experiences, or daily routines. They may experience clinical worsening as they attempt to make any recommended behavioral changes.

**Risk Minimization:** Intervention facilitators will be sensitive to the needs of participants and available for support by phone on a daily basis, if needed. Weekly, the study medical monitor ([name], JD, MSN, PMHNP-BC) will review participants' medication status and depressive and/or anxious symptom scores and ensure referral to appropriate care for those who show evidence of substantial worsening.

**Activity:** Administration of visual or auditory stimuli related to cognitive/emotional functions, including the use of words with negative affective valence, which may be emotionally-charged in content and relate to themes that patients with affective disorders often express. Control words will be affectively neutral and matched for word length, number of syllables, etc. with emotionally-laden words.

**Risk(s):** Some stimuli may be perceived as distressing by a given participant due to that participant's underlying perceptual or emotional impairment.

**Risk Minimization:** Stimuli will be thoroughly vetted by the research team. If the PI thinks that exposure to certain stimuli would be troubling or clinically inadvisable to a certain participant, s/he will not participate in this portion of the study. Those who partake in these tasks will always be monitored and the experimental session will be discontinued if a participant is noticeably uncomfortable or if s/he reports wishing to stop for any reason.

**Activity:** fMRI

**Risk(s)/Risk Minimization:**

(1) *Claustrophobia:* Despite efforts to ensure participants' comfort during scanning time (e.g., through staying in constant communication, minimizing the amount of time in the scanner, etc.), those who have claustrophobia may experience distress or perturbation of their psychiatric illness as a result of being confined and tasked to remain still in the scanner.

*Risk Minimization:* Prospective participants who disclose a history of claustrophobia will be excluded from the study.

(2) *Pregnancy:* There are no known risks of having MRI scans without contrast while pregnant; however, there may be risks that are unknown.

*Risk Minimization:* Prospective participants who are currently pregnant will be excluded from the study. Female participants of childbearing potential will take a urine test on the day of scans and be withdrawn from the study if pregnant.

(3) *Routine MRI Contraindications:* The magnetic field created by the scanner may interfere with the functioning of electromechanical devices (e.g., pacemakers) or cause temperature elevation in adjacent tissues in participants with implanted metal parts, including hip replacements, surgical clips, or metallic implants/fragments.

*Risk Minimization:* Participants will be carefully screened for all of the aforementioned, both at prescreen and on the day of scans, and excluded from the study.

(4) *Collision Hazard:* Because there is a strong magnetic field surrounding the scanner, there is potential for a metallic object to project toward the scanner and collide with a study participant. Such a collision could cause serious injury.

*Risk Minimization:* Participants and personnel will be carefully screened and instructed to remove all metal from their clothing/pockets and from their person before entering the scanning environment.

(5) *Noise:* The scanner produces tapping sounds during operation, which may reach very loud levels.

*Risk Minimization:* Participants will be provided with disposable earplugs that suppress external noise levels but do not eliminate voice communication with the scanner operator. In some cases, participants may use headphones instead, which will deliver other sounds and suppress scanner noise. If the participant finds the scanner noise objectionable, s/he can stop the study at any time.

(6) *Neurostimulation:* Due to the rapid switching of magnetic field gradients used in scanning, it is possible for participants to experience neurostimulation effects, such as muscle twitches and tingling sensations. Stimulation of the muscles of the heart, causing an abnormal heart rhythm, is much less likely to occur.

*Risk Minimization:* There are no known risks associated with these effects. The machines used in this research create magnetic field gradients within acceptable limits specified by the FDA.

(7) *Change in Body Temperature:* A slight, but not serious, increase in body temperature may occur in the presence of radiofrequency waves.

*Risk Minimization:* A significant, deleterious increase in temperature is extremely unlikely at the

settings employed in this study, which are within FDA guidelines.

(8) *RF Antenna Effects:* If metal wires or electrodes are attached to a participant's skin, radiofrequency signals from the scanner could induce sufficient electrical currents in the wires to cause burns.

*Risk Minimization:* If metal wires or electrodes are present, the scanner operator will inspect and arrange them to reduce potential for induced currents.

(9) *Quench Hazard:* The scanner uses liquid nitrogen and/or liquid helium to maintain the magnet's superconductivity. In the very remote event that the magnet quenches (loses its superconductivity), the liquid nitrogen and helium will boil off rapidly. Gaseous nitrogen and helium can be dangerous if breathed for more than a few moments.

*Risk Minimization:* Noxious gases would be vented to the outside of the imaging facility, per the design of the scanner. Oxygen monitors are present as an additional precaution. If necessary, the scanner operator will be present to provide immediate assistance to anyone inside/evacuate the scanning room.

(10) *Incidental Findings:* Although the pulse sequences used in this study are not those used for clinical diagnostic purposes, there is slight potential for incidentally uncovering structural brain pathology.

*Risk Minimization:* In the event an abnormality is detected by researchers or the scanning operator, the scans will be further examined by a radiologist and the PI may encourage the participant to consult his/her physician.

## **7.0 Reporting of Adverse Events or Unanticipated Problems involving Risk to Participants or Others**

Participants could react adversely during the assessment and/or intervention procedures or symptoms could worsen during the course of the study (although this worsening may or may not be related to the treatment). Once weekly during the eight-week MBCT or MBSR intervention, participants will complete a brief medication questionnaire, the Beck Depression Inventory-II, and the Spielberger State-Trait Anxiety Inventory. The PI and study coordinator will examine weekly medication status and symptom scores with the appointed study medical monitor ([name], JD, MSN, PMHNP-BC) and note changes. If we see evidence of substantial worsening, at-risk participants will be removed from the study and appropriate safety measures will be taken. Dropout rates will be examined at least quarterly, depending on enrollment. If there are concerns about attrition, the research team will review information regarding each participant who withdrew and study procedures, and ensure adequate subject protection and data integrity.

Reporting of adverse events will occur as follows:

During the study, if patients become unstable, [name], the Psychiatric mental health nurse practitioner, will be monitoring clinical change and risk of suicidality.

Any serious adverse event (e.g., death, suicide attempt, hospitalization) will be reported by telephone within 24 hours to the IRB and the DSMB. A full written report of the event will be sent to these entities within 24 hours of the event's occurrence.

Any moderate adverse event (e.g., causing interference with usual activities or requiring treatment) and which appears definitely, probably, or possibly related to study participation will be reported to the IRB and DSMB in writing within seven working days. Any mild adverse event will be summarized in the IRB annual progress reports.

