## Contemplative Neuroscience & Integrative Medicine Laboratory

- Deliberate awareness of routine activities and events such as: eating, weather, driving, walking, awareness of interpersonal communications

f) Daily home assignments including a minimum of 45 minutes per day of formal mindfulness practice and 5-15 minutes of informal practice, 6 days per week for the entire duration of the course

g) Individual and group dialogue and inquiry oriented around weekly home assignments including an exploration of hindrances to mindfulness and development and integration of mindfulness-based self-regulatory skills and capacities

h) Incorporation of exit assessment instruments and participant self-evaluation in Class 8

- Total in-class contact: 30+ hours
- Total home assignments: minimum of 42-48 hours
- Total group Orientation Session time: 2.5 hours

Mindfulness-based Cognitive Therapy (MBCT) (Appendix B). 8-week MBCT treatment protocol is standard as defined by Segal, Williams and Teasdale(Segal, Williams et al. 2013) with some minor modifications to address suicidality and presence of acute symptoms, i.e., introduction of crisis plans and cognitive components addressing suicidal cognitions and hopelessness. MBCT uses core meditation techniques (i.e., focused attention, open monitoring, body scan, breathing space, yoga) with a focus on mindful awareness as its core therapeutic ingredient and adds components of cognitive behavior therapy (CBT) (Segal, Williams et al. 2013).

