## 4.0 Enrollment/Randomization

Pre-screening questionnaire using REDCap will be assessing eligibility criteria for the multiple diagnostic arms and methodologies in this study. Suicidal ideation is probed in the BDI-II (item 9) administered in the pre-screening questionnaire and in weekly assessments. Endorsement of any response other than a 0 (indicative of no suicidal ideation) will automatically prompt an email alert to the PI, the study coordinator, [name], JD, MSN, PMHNP-BC (psychiatric nurse practitioner who has 12+ years of experience diagnosing and treating people with a wide range of psychiatric disorders, including depression), and [name]., clinical psychologist at the Osher Center. Follow-up to assess risk and clarify an action plan for protecting the participant will occur within 24 hours and is detailed in the attached suicide safety plan.

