### **Daily Survey**

**Home Meditation Practice** [daily during intervention]: Participants will be asked to record the frequency and duration of formal home practice sessions, which will take roughly 1-2 minutes to complete daily for eight weeks.

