### **Weekly Survey**

**Treatment Regimen Check-In** [weekly during intervention, posttest visit]: Participants will be asked to report whether their depression and/or anxiety medication regimen has changed or if any new, additional treatments have been initiated within the past week, which will take roughly 1-3 minutes to complete once weekly for eight weeks.

**Beck Depression Inventory-II** (BDI-II; Beck et al., 1996) [initial screening, weekly during intervention, posttest visit]: A 21-item measure that evaluates key affective, cognitive, and neurovegetative symptoms of depression listed in the *Diagnostic and Statistical Manual of Mental Disorders—Fourth Edition* (DSM-IV; American Psychiatric Association, 1994) and takes roughly 5-10 minutes to complete.

**Spielberger State-Trait Anxiety Inventory** (STAI; Spielberger et al., 1983) [initial screening, weekly during intervention, posttest visit]: A 40-item inventory that measures presence and severity of current anxious symptoms (i.e., state anxiety) and a general propensity to be anxious (i.e., trait anxiety). It takes roughly 5-10 minutes to complete.

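### As described, no weekly or daily form during the course asks about new or worse physical problems, although section 7.0 requires untreated moderate and mild events to be reported

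*Combined protocol and SAP*

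**What the plan says.** **During the course.** Section 7.0 lists the weekly safety set for MBCT and MBSR alike: "participants will complete a brief medication questionnaire, the Beck Depression Inventory-II, and the Spielberger State-Trait Anxiety Inventory". Under Weekly Survey (section 5.0), the treatment check-in asks "whether their depression and/or anxiety medication regimen has changed or if any new, additional treatments have been initiated within the past week". The BDI-II covers depressive symptoms, including neurovegetative ones, and the STAI covers anxiety. Under Daily Survey, "Participants will be asked to record the frequency and duration of formal home practice sessions".

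**Who looks at the answers.** Section 6.0 says that each week the medical monitor "will review participants' medication status and depressive and/or anxious symptom scores" and arranges referral for those who are substantially worse. Section 7.0 has the investigator and coordinator look at the same information with the monitor.

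**What must be reported.** Section 7.0 sets a written report to the IRB and DSMB within seven working days for "Any moderate adverse event (e.g., causing interference with usual activities or requiring treatment") if at least possibly related to participation. It adds: "Any mild adverse event will be summarized in the IRB annual progress reports".

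**Other relevant text.** The PROMIS pain items and the Pain Catastrophizing Scale are listed in section 5.0 for pre-testing, post-testing and follow-up, not weekly. Both courses include yoga: section 1.0 lists gentle Hatha yoga for MBSR and says "MBCT uses core meditation techniques (i.e., focused attention, open monitoring, body scan, breathing space, yoga") for the other course.

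**The concern.** A reporting duty works only if there is a way to find the events. The forms described for the eight weeks are built around mood, medication and practice adherence. An untreated back or joint strain that limits someone's activities, if possibly related to the course, falls within the moderate category in section 7.0. No described form asks about it, and it is not among the things the monitor is said to review each week.

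Such events are plausible. Yoga is part of both courses, MBSR asks for at least 45 minutes of formal practice at home on six days a week, and Figure 1's legend expects people with pain in the MBSR group. Non-serious events that the protocol's own rules require to be reported or summarized may go unrecorded or reach the monitor late.

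**Working it through.** The protocol gives no figure to reproduce on this point. The check is an inventory, followed by the cost of the remedy.

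**Step 1. Forms and reviews during the eight weeks.**

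| Item | Where described | Content | General question on physical problems? |
|---|---|---|---|
| Daily log | 5.0, Daily Survey | Home practice | No |
| Treatment check-in | 5.0, Weekly Survey | Depression/anxiety medication changes; new treatments | No; a treated event may show indirectly |
| BDI-II | 5.0, Weekly Survey | Depressive symptoms | No; some bodily symptoms of depression |
| STAI | 5.0, Weekly Survey | State and trait anxiety | No |
| Monitor's weekly review | 6.0 | Medication status, mood scores | No |

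**Step 2. Compare with the reporting rules in section 7.0.** The definition of a moderate event joins interference with usual activities and need for treatment by 'or'. So there are two cases:

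- Physical event that led to new treatment: the check-in may catch it. If its treatment item is meant only for depression or anxiety treatment, even this route is narrower.
- Physical event without new treatment, moderate by interference or merely mild: no described form asks.

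**Step 3. Other routes.** MBSR group dialogue centres on home assignments (1.0). Facilitator phone support is offered as needed (6.0), so the participant must start it. Instructors' stated safety role is judging suicidality (8.0). Termination for medical instability rests on the patient's own physician (8.0) and concerns severe cases. Case review of withdrawals depends on concern about attrition (7.0). Posttest and follow-up pain scales could show worse pain afterwards, but no safety review of them is described. None of these is described as a way of ascertaining adverse events during the course.

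**Step 4. Size and cost of adding one question.** Inputs are the planned arm sizes in 9.0 (42 anxiety, 26 depression, 30 stress/chronic pain) and the completion times under Weekly Survey. The one-minute time and the 'yes' rates are assumptions.

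- Patients: 42 + 26 + 30 = 98 at most; fewer if one person counts in two arms.
- Administrations per person: 8 weekly + 1 posttest = 9.
- Total: 98 × 9 = 882, fewer with dropout.
- Time: 9 minutes per participant; 882 ÷ 60 = 14.7 hours in all.
- Current weekly survey: (1 + 5 + 5) to (3 + 10 + 10) = 11 to 23 minutes. One more minute adds 1/23 = 4.3% to 1/11 = 9.1%.
- 'Yes' answers to grade: at 2%, 0.02 × 882 = 17.6; at 10%, 0.10 × 882 = 88.2; at 30%, 0.30 × 882 = 264.6.

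**The case against.** The strongest reply is proportion. Section 6.0 calls physical risk minimal, the yoga is gentle, and participants must already have registered for the course before prescreening. The blood draws and scans take place at pre- and post-testing, outside the weekly window. Worse pain could show on the posttest or follow-up scales, and participants can raise problems in class or by phone. All of this stands, and it keeps the point at the level of a cheap improvement. It does not supply a means of finding the events that section 7.0 covers.

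A second reply is that the forms are described, not reproduced. This also stands. The check-in form, Appendices A and B and the suicide safety plan were not available, and the four assessment points in the stress-arm power calculation (9.0) are undated, so a mid-course assessment in that arm is not excluded. The conclusion is therefore limited to the plan as described.

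A third reply is burden. People selected for depression, anxiety, stress or pain may answer 'yes' often. That is fair, so the working goes up to 30%, and the question is kept to physical problems because the BDI-II and STAI already cover emotional ones.

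Three stronger readings are tempting and not supported:

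- *The seven-working-day limit would be breached.* Section 7.0 does not say whether the period runs from the event or from awareness of it.
- *The pilot's count of physical events would be misread as evidence of safety.* None of the six aims in section 2.0 concerns safety, and the protocol proposes no such inference.
- *The study collects nothing on bodily symptoms.* The BDI-II includes neurovegetative symptoms, and pain is measured before and after the course.

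**Conclusion.** The point holds in a limited form and is worth considering. As described, systematic elicitation during the course covers mood, anxiety and treatment changes but not physical problems, in either course. Untreated, non-serious physical events, including some that section 7.0 makes reportable, would come to light mainly if volunteered, or indirectly and later through pain scales with no described safety review.

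The number of missed events cannot be estimated from the documents, and no estimate is offered. The likely harm is modest on the protocol's own assessment of physical risk. A reader might infer that participants are exposed to an unmonitored serious hazard. The text does not support that: serious events have their own 24-hour reporting rule, and the gap concerns non-serious, untreated ones. The conclusion assumes that the unseen form and appendices contain no such question.

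**What to change.** Add one open question to the existing Weekly Survey and to posttest: *Since the last survey, have you had any new or worse physical problem, injury or hospital visit? If yes, describe.* Send any 'yes' to the study coordinator and medical monitor for grading under section 7.0. The routing has a model in section 4.0, where a non-zero answer to BDI-II item 9 "will automatically prompt an email alert to the PI, the study coordinator" and clinicians. Report elicited and volunteered events separately.

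**Cost.** About 9 minutes per participant and at most 14.7 hours of participant time over the study, with no new visits.

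**Downside.** More mild events to grade and list: about 18 to 88 'yes' answers at an assumed 2% to 10%, and about 265 at an assumed 30%. Grading would fall to existing staff, and its time is not costed here because the documents give no basis for it.

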## 8.0 Study Withdrawal/Discontinuation

### **Criteria for study termination**

Patients will be terminated from the study if they meet the following criteria:

- 1) Patient exhibits psychopathology requiring changes in medication dosage or type
- 2) Patient requires inpatient hospitalization or medication
- 3) Patient becomes medically unstable and necessitates intensive medical intervention as determined by the patient's physician
- 4) Patient becomes suicidal as determined by MBI instructors and requires inpatient hospitalization or more intensive treatment
- 5) Patient misses more than 50% of MBI sessions (determined to be an adequate dose)(Crane and Williams 2010).

Patients terminated because of exacerbation of symptoms will be considered treatment non-responders, whereas patients terminated due to medical problems or suicidality may participate again once they are medically and psychologically stable. They will be enrolled in a subsequent group at a later time.

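### Sections 6.0, 7.0 and 8.0 are not aligned on what happens to a patient who worsens substantially, and removing such patients would bias the pre-post analyses towards improvement

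*Combined protocol and SAP*

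**What the plan says.** Four sections of the combined protocol and SAP bear on a patient who deteriorates.

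- **Section 7.0 (adverse events).** Medication status, BDI-II and STAI are reviewed weekly. On substantial worsening the rule is: "at-risk participants will be removed from the study and appropriate safety measures will be taken". The psychiatric nurse practitioner "will be monitoring clinical change and risk of suicidality".
- **Section 6.0 (risks).** The medical monitor reviews the same weekly information and will "ensure referral to appropriate care for those who show evidence of substantial worsening". Removal is not mentioned. On item 9 of the BDI-II, the rule is: "Endorsement of any response other than a 0 (indicative of no suicidal ideation) will automatically prompt an email alert to the PI". The alert also goes to the coordinator, the nurse practitioner and a clinical psychologist. Section 4.0 repeats this, and both sections refer to an attached suicide safety plan for the follow-up.
- **Section 8.0 (termination).** None of the five criteria is worsening as such. The nearest is "Patient exhibits psychopathology requiring changes in medication dosage or type". Criterion 4 reads: "Patient becomes suicidal as determined by MBI instructors and requires inpatient hospitalization or more intensive treatment". The paragraph below the list adds: "Patients terminated because of exacerbation of symptoms will be considered treatment non-responders".
- **Section 9.0 (statistics).** It gives sample-size arguments for continuous ERP, fMRI and go/no-go measures, and names a repeated-measures ANCOVA for the fMRI data. It gives no analysis population, no missing-data method and no handling of removed patients.

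No section defines substantial worsening. The Weekly Survey part of section 5.0 schedules BDI-II and STAI at screening, weekly and at the posttest visit.

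**The concern.** Whether a worsening patient stays in the study depends on which section the staff member follows. Someone who refers the patient and keeps them in satisfies section 6.0 and meets no criterion in section 8.0 (unless a listed event occurs), but does not do what section 7.0 says.

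The choice also affects the results. Removal under section 7.0 is informed by symptom scores that are themselves study measures. If removed patients give no posttest, the people who did worst are missing from the pre-post comparison, and the remaining mean moves towards improvement. No untreated control arm is described against which such a shift could be seen.

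**Working it through.** **1. The sections side by side**

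| Section | Trigger | Action |
|---|---|---|
| 6.0 | substantial worsening | referral |
| 7.0 | substantial worsening | removal plus safety measures |
| 8.0, criteria 1 to 5 | worsening not listed; criterion 1 needs a medication change | termination |
| 8.0, paragraph after the list | exacerbation of symptoms | termination presumed; counted as non-responder |

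The first two rows share a trigger and differ on whether the patient leaves. The last row presumes a ground that the list above it does not contain.

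**2. The one stated figure that removal touches**

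Section 9.0 needs 34 evaluable patients in the Anxiety Arm and allows 18% attrition: 34 / (1 − 0.18) = 41.46, rounded up to 42. This reproduces the stated 42. The 34 cannot be rebuilt, because the means and SDs behind it are not given. The 18% is not broken down by reason, so the documents give no rate of removal for worsening.

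**3. Size of the bias, as an illustration**

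Assumptions, none of them document figures: change scores are normal; exactly the worst-changing fraction p on the trigger score is removed; removed patients give no posttest; an outcome's change correlates ρ with the trigger's change.

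Shift of the retained mean towards improvement, in SD of change = ρ × φ(z) / (1 − p), where z is the normal quantile cutting off the worst fraction p.

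- p = 0.05: 0.1031 / 0.95 = 0.109
- p = 0.10: 0.1755 / 0.90 = 0.195
- p = 0.15: 0.2332 / 0.85 = 0.274
- p = 0.18: 0.2624 / 0.82 = 0.320 (every planned loss is a removal for worsening, an extreme)

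| Removed | ρ = 1 (trigger is the outcome) | ρ = 0.5 | ρ = 0.3 | ρ = 0 |
|---|---|---|---|---|
| 5% | 0.109 | 0.054 | 0.033 | 0 |
| 10% | 0.195 | 0.097 | 0.058 | 0 |
| 15% | 0.274 | 0.137 | 0.082 | 0 |
| 18% | 0.320 | 0.160 | 0.096 | 0 |

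In an arm of 42, 5% to 15% is 42 × 0.05 = 2.1 to 42 × 0.15 = 6.3 patients.

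**4. Effect on a test of no change**

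Simulation: 40,000 runs, 42 patients, true mean change zero, two-sided one-sample t-test on those retained, nominal 5% error.

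| Removed | ρ = 1 | ρ = 0.5 | ρ = 0.3 | ρ = 0 |
|---|---|---|---|---|
| 5% | 10.3% | 6.4% | 5.5% | 4.9% |
| 10% | 26.5% | 9.1% | 6.4% | 5.0% |
| 18% | 65.5% | 15.8% | 8.6% | 5.1% |

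The ρ = 1 column applies to BDI-II or STAI analysed as outcomes. Section 5.0 names DASS-A as the primary anxiety measure, and section 9.0 sizes the arms on ERP, fMRI and go/no-go. For all of these ρ is unknown and below 1.

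**The case against.** **Removal and referral can coexist.** Referral is a natural example of section 7.0's safety measures, and staff who do both satisfy both sections. This stands: a reader might infer a flat contradiction, and the text does not support that. What remains is that a patient who is referred and kept in is handled according to one section and not the other.

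**Section 8.0 does contemplate worsening.** Its non-responder sentence fits section 7.0 and says how such patients count. This stands in part. It would limit the bias for a responder endpoint, but none is defined, and the analyses described are of continuous pre-post measures.

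**Suicidality.** A reader might infer that different people hold conflicting authority. The documents do not show this. The item 9 alert with its 24-hour follow-up, the nurse practitioner's monitoring, and criterion 4 are different functions. Criteria 1 and 2 need no instructor's judgement. The safety plan, which is not among the documents, may settle who decides. What survives is only that criterion 4 names instructors alone and should be checked against the other sections and that plan.

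**Magnitude.** A reader might set the 0.11 to 0.27 SD against the change of about 0.50 SD that 34 patients could detect with a two-sided paired t-test at 80% power. That comparison is unsound. The 34 concerns P1 amplitude, not BDI-II or STAI, so it would presume a correlation of 1. Section 9.0 also states neither the test nor its sidedness. Removal of exactly the worst fraction is a worst case as well.

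**Conclusion.** The point holds as a matter of alignment and missing-data handling. Substantial worsening is undefined, sections 6.0, 7.0 and 8.0 do not agree on whether it ends participation, and section 9.0 does nothing to offset selection on symptom scores if it does.

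The direction of the bias is clear where an outcome's change is positively related to the trigger's: apparent improvement is overstated. Its size cannot be computed from the documents. Under the stated assumptions it is 0.11 to 0.27 SD for 5% to 15% removed when the trigger score is the outcome, and that multiplied by the correlation for DASS-A, P1, fMRI or go/no-go. The documents do not support a claim that patients are left without a safety response, or that the powered endpoints are biased by any particular amount.

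**What to change.** 1. **Reconcile the text.** The sponsor's clinicians should align sections 4.0, 6.0, 7.0 and 8.0, and the suicide safety plan, so that trigger, decision-maker and action agree wherever they appear. Which rule to adopt is for them; none is proposed here.
2. **Separate stopping from data collection.** Whatever action is chosen, invite removed patients who are willing and able to complete the posttest self-report remotely.
3. **Self-report outcomes.** State in section 9.0 that they are analysed in a repeated-measures mixed model using all available weekly and posttest scores, and not by carrying the last score forward. For BDI-II and STAI the weekly scores that informed removal are then in the model. DASS-A is not in the weekly survey, so for it the remote posttest matters most.
4. **ERP, fMRI and behavioural endpoints.** A questionnaire cannot replace these. Report the number removed for worsening in each arm, state that results are for completers, and add a sensitivity analysis that assumes a range of less favourable changes for those removed.

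The cost is protocol wording, remote questionnaires for a few patients and a little more analysis.
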